8.4.4. Open-Label Study Reporting Results

In order to reduce operational bias that can be introduced during the analysis, while the study is ongoing summary statistics by treatment groups across all sites will be limited to a small analytical group at the Sponsor not involved in the daily operations of the study. Treatment groups will be masked in the summary outputs (tables, listings, and figures) in order to reduce the inference should results be inadvertently accessed. The limited results of the interim analysis will be shared with Investigators and IRBs as necessary to conduct the study.

Upon study completion, the full results will be shared with all investigators and clinical sites.

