10.4. Data Handling

KCI is responsible for compilation and verification of the clinical study data, retention of the clinical study database, performance of statistical analysis, and preparation of the clinical study report.

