2.1 Sample Size and Power

The primary endpoint of this study is the subject incidence of SSC. The incidence rates of SSC are different for septic and aseptic revisions; the assumed SSC rate is 33% for septic and 6.9% for aseptic. This study plans to enroll at least 50% septic revisions overall. These enrollment rates lead to an assumed pooled SSC rate of 20% in the SOC dressing arm.

Assuming an overall type 1 error rate of 0.05, with a two-sided hypothesis test, the study will have at least 80% power to detect a difference of 10% (50% reduction) in SSCs in the ciNPT arm with 199 subjects in each treatment arm, with one interim analysis at about 50% of the evaluable subjects for a total of 398

subjects using the likelihood ratio test. With an estimated 5%-10% loss, a non-binding interim analysis for superiority at approximately 50% of the evaluable subjects using O'Brien-Fleming method for monitoring boundaries, the planned sample size will be inflated for a potential loss of follow-up for a total of 440 subjects.

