6 INTERIM ANALYSIS

As stated in the protocol, an interim analysis will be conducted at information-time $t=0.5$, i.e., when approximately half the planned study subjects have had their primary endpoint assessed. The interim analysis will be performed at the $\alpha=0.0052$ level; if the p-value for the primary endpoint is < 0.0052 , the study will be stopped, and the null hypothesis rejected. Otherwise, the final analysis will be conducted at $\alpha=0.048$ (i.e., by constructing a 95.2% confidence interval) to preserve overall Type I error rate at 5%. These α values were chosen using an O'Brien-Fleming α -spending function assuming $t = 0.5$. The alpha levels that will be used at the interim and final will be calculated according to the precise information time at the interim analysis.

If warranted, based on the unblinded interim results, the final sample size may be increased using the appropriate statistical methodology as described in Chen et al. [2004]². Per Section 8.4.5 of the study protocol, it stated the increase to the final sample size would only occur if the interim results had a conditional power of success $\geq 50\%$, would be subject to the restrictions in Chen et al. [2004]², and

would not be considered statistically binding. However, the interim SAP further clarified that an increase to the final sample size could occur if the conditional power is below 50%. If the sample size is increased when conditional power is $\geq 50\%$, a type I error rate would not be inflated as mentioned in Chen et al. [2004]². If the sample size is increased when conditional power is $< 50\%$, an adjustment will be needed to control the Type I error. The adjustment was outlined in Section 7.3 of the interim SAP.

At the interim analysis, the rate of SSC for septic and aseptic revisions will be examined to confirm assumptions of the sample size calculations. In addition, the rate of SSC will be independently assessed for septic and aseptic revisions at the interim analysis to determine if a modification of enrollment from a 1:1 ratio of septic or aseptic revisions to focus on enrollment for either revision type is needed.

In the final analysis, the type I error rate ($\alpha=0.048$) for statistical significance will be used for the primary and secondary analyses using the O'Brien-Fleming method per study protocol.

Both, the interim SAP and the interim analysis results, will be included in the final clinical study report for this study.

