Decisions and/or results from the interim analysis may affect the planned final data analysis. Therefore, this SAP may be amended after the interim analysis and before the final study database lock if necessary. Any changes will be documented appropriately in the corresponding Sections like "DOCUMENT HISTORY" and Section 10 "Changes from Planned Analysis".

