The first test will utilize all subjects from the mITT combined population included in the interim and subjects post-interim. The second test will utilize only the post-interim mITT subjects from either the septic or aseptic population depending on the results and/or decision from the interim analysis. The second test will be performed only if the test 1 is statistically significant at the 0.048 level.

Case 1 Did Not Enrich	Case 2 Enriched with Septic	Case 3 Enriched with Aseptic

 • Test 1: Adaptive test of H_0 (Combined population) 	
 • Test 1: Adaptive test of H_0 (Combined population) • Test 2: standard test of H_0 (post-interim population only) 	
 • Test 1: Adaptive test of H_0 (Combined population) • Test 2: standard test of H_0 (post-interim population only)

For Case 1, if the 2-sided p-value from the test 1 is ≤ 0.048 and the SSC rate of the ciNPT arm is lower than the SSC rate of SOC arm, then the null hypothesis is rejected; superiority in effectiveness of the ciNPT arm compared with the SOC arm will be established. However, for Case 2 or Case 3, both test 1 and test 2 must reject the null hypothesis at the 0.048 level in order to claim statistical significance.

Additionally, figure(s) may be generated to display the results from the analyses of the primary endpoint graphically.

Supportive/exploratory analyses of the primary efficacy endpoint described below in Section 8.5.1 will be performed on the mITT analysis set unless otherwise specified.

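### SAP 6 lets unblinded interim results, not only the planned interim decisions, prompt amendment of the final analysis, so the 5% error rate is assured only for the pre-specified adaptations

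*SAP*

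**What the plan says.** The closing paragraph of SAP Section 6 states "Decisions and/or results from the interim analysis may affect the planned final data analysis" and continues "Therefore, this SAP may be amended after the interim analysis and before the final study database lock if necessary". The only conditions are timing, necessity and documentation (document history and SAP Section 10).

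The same section sets the interim level at 0.0052; if it is crossed, "the study will be stopped, and the null hypothesis rejected". Otherwise the final level is 0.048, with both levels to be recalculated for the actual information time. A sample size increase at conditional power below 50% is to carry a Type I error adjustment, set out in Section 7.3 of the interim SAP. SAP 8.5 adds closed testing if one revision type is enriched: in Cases 2 and 3 "both test 1 and test 2 must reject the null hypothesis at the 0.048 level in order to claim statistical significance".

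On access, Protocol 8.4.4 says that by-arm summaries "will be limited to a small analytical group at the Sponsor not involved in the daily operations of the study", with treatment groups masked in the outputs; limited interim results may go to Investigators and IRBs. Protocol 10.4 makes the sponsor responsible for "performance of statistical analysis, and preparation of the clinical study report".

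**The concern.** The planned decisions already have rules, so a clause that adds results as a separate ground for amendment reaches beyond them. It does not exempt the primary endpoint, analysis set, test or strata.

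The pair 0.0052 and 0.048 holds the overall rate at 5% for two looks at one statistic fixed in advance. It does not cover a final statistic chosen because of what half the by-arm data showed, and recording the change afterwards does not restore the rate.

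The plan contains alternatives to switch to: ITT, mITT, PP and mPP sets; randomised or actual revision type; stratified or unstratified tests; and combined, septic and aseptic populations. The interim looks at septic and aseptic rates separately, so the population switch is the one that its results would most naturally suggest. In an open-label trial analysed by its sponsor, a reader of the report could not rule out that a late amendment followed the data.

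**Working it through.** **Inputs from the documents.** Overall level: "Assuming an overall type 1 error rate of 0.05, with a two-sided hypothesis test" (SAP 2.1). Interim level 0.0052 at t = 0.5 and final level 0.048 (SAP 6 and 8.5). Loss to follow-up 5% to 10% (SAP 2.1).

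**Step 1: reproduce the plan's figure.** The critical values are z1 = 2.794 (for 0.0052) and z2 = 1.977 (for 0.048). With t = 0.5, the overall two-sided error is

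1 − ∫ from −z1 to z1 of φ(x)·[Φ((z2 − √t·x)/√(1−t)) − Φ((−z2 − √t·x)/√(1−t))] dx = 0.0500.

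The stated 5% is reproduced for a fixed statistic. Holding 0.0052 and 0.048 while the interim falls at t = 0.4 or 0.6 gives 0.0507 or 0.0494, so timing drift is minor, and the plan recalculates for it anyway.

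**Step 2: the planned adaptations.** These are simulations under the null.

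- Sample size increase only at conditional power of at least 50%, with the second stage 2 to 5 times the plan (assumed): overall two-sided error 0.044 to 0.037, below 0.05.
- Enrichment with both tests required: about 0.014.
- Sample size increase at conditional power below 50% with no adjustment: 0.058 to 0.065 for a second stage 2 to 5 times the plan. The SAP says this case will be adjusted; the adjustment is in the interim SAP, which is not among the documents.

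**Step 3: switching among close variants, by amendment.** For each variant k, let X_k and Y_k be the first- and second-stage z statistics, with correlation ρ between variants and final Z_k = (X_k + Y_k)/√2. Stop early on the planned statistic at 0.0052. Otherwise take the variant with the largest X_k and claim benefit if Z_k > 1.977. One-sided false-claim rates (2 million runs):

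| Variants | ρ = 0.99 | ρ = 0.95 |
|---|---|---|
| 1 (no switch) | 2.5% | 2.5% |
| 2 | 2.7% | 3.0% |
| 4 | 2.9% | 3.5% |

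The correlations are assumptions, with this support. For nested sets the correlation is about √(n_subset/n). With 5% to 10% loss, mITT against ITT gives √0.95 = 0.97 to √0.90 = 0.95. In simulation at 199 per arm under the null, stratified and unstratified statistics correlate at 0.9997. True strata and strata with 5% misclassified (assumed) correlate at 0.994.

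**Step 4: switching the population, by amendment.** Let s and a be independent septic and aseptic statistics and let the combined statistic be √w·s + √(1−w)·a, where w is the septic share of information. Take whichever of the three looks best at the interim and test all its data at 0.048. One-sided rates are 4.83% at w = 0.5 and 4.79% at w = 0.776, about 4.8% against 2.5%. If the choice is by absolute size, the two-sided rate is 8.7% to 8.9% against 5%.

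**Step 5: which changes have a control.** The supplied documents name one for information time, for sample size and for enrichment by Cases 1 to 3. They name none for a change of analysis set, test, strata or population made by amendment.

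**The case against.** The best defence is context. The sentence directly follows the sample size and enrichment rules, each of which does change the final analysis, so it may mean only that the interim selects among Cases 1 to 3. The primary analysis is already named: mITT, with a CMH test stratified by randomised revision type. SAP 8.5.1 labels the other sets, actual revision type and the unstratified test as additional or sensitivity analyses. Protocol 8.4.4 restricts and masks by-arm output, disqualifying deviations are defined blinded to treatment, and Protocol 8.3.4 gives 0.048 only as an example when the sample size is unchanged. The interim SAP, to be finalised before the interim, may contain a firewall.

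Much of this stands. It rules out saying that the 5% rate is unprotected overall, and it makes large inflation from the near-identical variants implausible. It does not remove the permission. The clause names results separately from decisions and has no scope limit. Masked labels still show which variant or population has the larger difference. The blinding rule for deviations has no counterpart for SAP amendments. Whether the interim SAP supplies one can be neither confirmed nor excluded.

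A reader might also infer that the version 2.0 changes listed in SAP Section 10, including which revision type the primary and secondary analyses use, were driven by interim results. The documents do not support that: they do not say whether those changes came before or after the interim, and they show no results-driven change to the primary test.

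**Conclusion.** The point holds in this form: the 5% rate is assured for the pre-specified adaptations, as far as their stated controls hold, and not for other changes to the primary test made because of interim results. The one-sided false-claim rate, against 2.5%, is about 2.7% to 3.5% for two to four close variants and about 4.8% for a population switch. These figures assume deliberate switching to the best-looking option with no change of level, and the first range also rests on the assumed correlations. They show what the wording would permit, not what was done. The part resting on the interim SAP, including its Section 7.3 adjustment, could not be checked.

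**What to change.** Replace the first two sentences of the closing paragraph of SAP 6 with text such as:

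> Only the pre-specified interim decisions (stop, sample size increase, Case 1, 2 or 3) carry into the final analysis, through the rules in this SAP and the interim SAP, including recalculation of the significance level for actual information time and any adjustment required by interim SAP Section 7.3. The primary endpoint, analysis set, test, strata and the rule for setting the level are fixed before by-arm interim data are produced. Later SAP amendments are written by staff without access to by-arm results; any other analysis changed because of interim results is reported as supportive.

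The text fixes the rule for the level, not the number, because SAP 6 requires recalculation; the flat 0.048 in SAP 8.5 should be aligned with that. Every planned adaptation survives. If the clause was meant only to select among Cases 1 to 3, this simply says so. The cost is a wording change, a small loss of flexibility, and the need to staff amendments with people who have not seen by-arm results.

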7 GENERAL STATISTICAL CONSIDERATIONS

7.1 General Considerations

- Data processing, tabulation of descriptive statistics, calculation of inferential statistics, and graphical representations will be performed primarily using SAS (release 9.4 or higher). If the use of other software is warranted, the final statistical report will detail software deployed along with their reasons for use.
- Summaries of continuous variables will show the number of non-missing values [n], along with the mean, median, standard deviation, minimum and maximum. In general, the maximum and minimum values will be presented to the same precision as the raw data; the mean and median will be presented to one decimal place more than the raw data. The standard deviation and confidence interval limits will be presented to two decimal places more than the raw data.
- P-values will be presented to four decimal places. A p-value less than 0.0001 will be presented as < 0.0001 or $< .0001$.
- The most recent assessment prior to TKA revision procedure will be used as the baseline reference for all analyses which incorporate a baseline value.
- Change from baseline will be calculated using the relevant post initial dressing application of either ciNPT or SOC value minus baseline value. Percent change from baseline will be calculated using change from baseline value divided by baseline value and multiplied by 100.

- Summaries of categorical (qualitative) variables will include the frequency and percentage of subjects. In general, the denominator for the percentage calculation will be based upon the total number of subjects in the study population, unless otherwise specified. Percentages will be presented to 1 decimal place unless otherwise specified.
- Other ad hoc data analyses to characterize the activity of the treatment may be conducted. These additional ad hoc analyses will be decided at the time of analysis. Ad hoc analyses will be identified in the output and the CSR and labeled as such.
- All collected data will be listed for all subjects who provided informed consent.
- For all exploratory endpoints, assessments performed outside the scheduled visit windows may not be included in the analysis but will be listed separately.

7.2 Conventions/Imputations for Adverse Events

For determination of treatment emergent adverse events only, the following analysis date conventions will be applied:

If the adverse event (AE) start date is partially missing [e.g. the month of the start date is missing, or the day of the date is missing], the following conventions will be applied:

- If only the day is missing then the imputed day will be: The day of the initial dressing/treatment application if the month is the same, or the first day of the month will be used if the month differs or the imputed day results in a start date after the end date.
- If only the month is missing then the imputed month will be: the month of the initial dressing/treatment application if the year is the same, or 'January' if the year differs.
- If both month and day are missing, then the month is imputed as the month and day of the initial dressing/treatment application. If the imputed day results in a start date after the end date, then the first day of the month will be used.

If the AE start date is completely missing and the end date is complete

- If the end date is on or after the date of the initial dressing application/treatment, the start date will be imputed as the date of the initial dressing application/treatment start.
- If the start date is completely missing and the end date is completely missing then the AE will assume to be "on-study", then the start date will be set to the date of the initial dressing application/treatment.
- If the start date is completely missing and end date is prior to the initial dressing application/treatment, the AE will assume to be 'prior to study' and not be included in any summaries.

7.3 Handling of Missing data/Dropouts

In general, missing data will not be imputed except for the followings:

- the date of AEs as described in Section 7.2 of this document

- the data imputation for sensitivity analyses for exploratory endpoints Pain, KOOS scores and PROMIS Global 10 as described in Sections 8.7.1, 8.7.2 and 8.7.3 respectively

8 STATISTICAL ANALYSES OF EFFICACY MEASURES

8.1 Subject Enrollment and Disposition

Summaries in this section, section 8.1, will be based on all subjects who provided informed consent. The summary of enrollment and subject disposition will include:

- All screened subjects who provided informed consent
- All randomized subjects – ITT analysis set (overall and by revision type)
- In ITT analysis set: All subjects who completed and discontinued from the study along with their reasons for discontinuation
- All randomized and treated subjects – Safety analysis set
- All subjects in mITT, PP, mPP and Safety analysis sets (overall and by revision type)

Additionally, figure(s) may be generated to display the enrollment and disposition summary graphically.

Summaries for all screen failure subjects or subjects excluded from any analysis sets will be provided as well. The summaries will include:

- All screen failure subjects along with the reason for failing screening
- All subjects excluded from mITT analysis set along with the reason for exclusion
- All subjects excluded from PP analysis set along with the reason for exclusion
- All subjects excluded from mPP analysis set along with the reason for exclusion
- All subjects excluded from Safety analysis set along with the reason for exclusion

8.2 Demographics and Baseline Characteristics

The summary statistics for demographics and baseline characteristics will be presented by treatment arm and overall. The summary tables will include:

1. Baseline demographics and other characteristics (e.g. age, race, sex, ethnicity, height, weight, body mass index (BMI)) will be summarized. Additionally, Age and BMI will be compared between the treatment arms using a 2-sample t-test. Race/ethnicity and sex will be compared between the treatment arms using Fisher's exact test or Chi-Square test as appropriate. This analysis will be based on the ITT analysis set.
2. Baseline comorbidities will be summarized based on both ITT and mITT analysis sets.
3. Characteristics for TKA revision procedure on Day 0 (e.g., type of TKA revision, TKA location, duration of TKA procedure derived by taking the difference of TKA procedure stop time and TKA procedure start time, material used, location, length of incision, method of closure) will be summarized based on the ITT analysis set.
4. All captured medical and surgical history will be coded using the MedDRA coding dictionary version 20.1 or higher and will be summarized based on the ITT analysis set. The following summaries will be presented:
 - Incidence of all medical and surgical history by System Organ Class and Preferred Term

- Incidence of medical and surgical history that can impact wound healing including immune suppressive disease or therapy, impaired nutritional status, Diabetes Mellitus I & II, active tobacco use, chronic obstructive pulmonary disease, peripheral vascular disease, lymphedema, malnutrition, congestive heart failure, and previous infections in operative site, iron or vitamin deficiency by System Organ Class and Preferred Term

8.3 Concomitant Medication Analysis

Concomitant medications/therapies are defined as medications taken during the study (during the 30 days preceding the Day 0 TKA revision through the final visit). The WHO Drug Dictionary released MAR2017 or later will be used for the coding of medications.

Listings for concomitant medications will be presented by subject. The number of subjects using concomitant medications will be summarized using the pharmacological subgroup name (ATC3) and preferred drug name based on the WHODrug medical coding dictionary. In any given category (e.g., ATC3 or preferred drug name) a subject will be counted only once. All subjects in the Safety analysis set will be accounted for in the summation. The following summaries will be presented by treatment arm:

- Incidence of all concomitant medications / therapies by pharmacological subgroup name (ATC3) and preferred drug name
- Incidence of pain killers/narcotics medications by pharmacological subgroup name (ATC3) and preferred drug name

8.4 Protocol Deviations

Protocol deviations will be defined as departures from the study protocol that could potentially affect clinical results or safety conclusions. All protocol deviations will be identified, recorded and presented in subject data listings. Following applicable KCI standard operating procedures, the Protocol Deviation Review Committee evaluates the protocol deviation data and identifies all important disqualifying protocol deviations prior to the final database lock. The results from the review will be imported and incorporated in the corresponding analysis.

All protocol deviations will be presented in subject data listings. Additionally, disqualifying protocol deviations for Per-Protocol analysis set will be subsequently presented in listings and will be summarized by coded term/description.

